8.3 ADVERSE EVENTS AND SERIOUS ADVERSE EVENTS

8.3.1 DEFINITION OF ADVERSE EVENTS (AE)

Adverse event means any untoward medical occurrence associated with the use of an intervention in humans, whether or not considered intervention-related (21 CFR 312.32 (a)).

8.3.2 DEFINITION OF SERIOUS ADVERSE EVENTS (SAE)

An adverse event (AE) or suspected adverse reaction is considered "serious" if, in the view of either the investigator or sponsor, it results in any of the following outcomes: death, a life-threatening adverse event, inpatient hospitalization or prolongation of existing hospitalization, a persistent or significant incapacity or substantial disruption of the ability to conduct normal life functions, or a congenital anomaly/birth defect. Important medical events that may not result in death, be life-threatening, or require hospitalization may be considered serious when, based upon appropriate medical judgment, they may jeopardize the participant and may require medical or surgical intervention to prevent one of the outcomes listed in this definition. Examples of such medical events include allergic bronchospasm requiring intensive treatment in an emergency room or at home, blood dyscrasias or convulsions that do not result in inpatient hospitalization, or the development of drug dependency or drug abuse.

8.3.3 CLASSIFICATION OF AN ADVERSE EVENT

8.3.3.1 SEVERITY OF EVENT

For adverse events (AEs) not included in the protocol defined grading system, the following guidelines will be used to describe severity.

- Mild Events require minimal or no treatment and do not interfere with the participant's daily activities
- **Moderate** Events result in a low level of inconvenience or concern with the therapeutic measures. Moderate events may cause some interference with functioning.
- **Severe** Events interrupt a participant's usual daily activity and may require systemic drug therapy or other treatment. Severe events are usually potentially life-threatening or incapacitating. Of note, the term "severe" does not necessarily equate to "serious".

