9.4.4 SAFETY ANALYSES

AEs will be reported by frequency and percentage of participants presenting with the outcomes. Specific side effects and adverse events of interest are listed with secondary outcomes (9.4.3). All other side effects and adverse events outside of those listed in 9.4.3 will also be reported by frequency and percentage. Other AEs will be reported by severity of the adverse events (mild, moderate or severe) and related or not related to the study protocol. AEs will be grouped by Medical Dictionary for Regulatory Activity (MedDRA) System Organ Class (SOC).

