10.1.2 STUDY DISCONTINUATION AND CLOSURE

This study may be temporarily suspended or prematurely terminated if there is sufficient reasonable cause. Written notification, documenting the reason for study suspension or termination, will be provided by the suspending or terminating party to study participants, investigator, the Investigational New Drug (IND) sponsor and regulatory authorities. If the study is prematurely terminated or suspended, the Principal Investigator (PI) will promptly inform study participants, the Institutional Review Board (IRB), and sponsor and will provide the reason(s) for the termination or suspension. Study participants will be contacted, as applicable, and be informed of changes to study visit schedule.

Circumstances that may warrant termination or suspension include, but are not limited to:

• Determination of unexpected, significant, or unacceptable risk to participants

- Demonstration of efficacy that would warrant stopping
- Insufficient compliance to protocol requirements
- Data that are not sufficiently complete and/or evaluable
- A life-threatening medical situation with determined study procedure causality
- Persistent or significant incapacity as a result of study drug(s) or procedure(s)
- A study participant with hepatic enzyme elevation greater than 3 times the upper limit of normal seen on laboratory testing on day 14

Study may resume once concerns about safety, protocol compliance, and data quality are addressed, and satisfy the sponsor, IRB and/or Food and Drug Administration (FDA).

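### Section 8.3.3.1 defers to a grading system the protocol does not contain, so a symptom-free liver-test rise would, read literally, be reported as mild whatever its size

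*Combined protocol and SAP*

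**What the plan says.** Section 8.3.3.1 opens by limiting its scope: the guide is for events "not included in the protocol defined grading system". Three levels follow.

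- Mild: "Events require minimal or no treatment and do not interfere with the participant's daily activities".
- The level above it, called moderate, is described in these terms: "Events result in a low level of inconvenience or concern with the therapeutic measures", with possible interference with functioning.
- Severe: events that interrupt usual activity and may need systemic or other treatment. The text adds that "Severe events are usually potentially life-threatening or incapacitating" and that severe need not mean serious.

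Section 8.3.4 has the clinician's severity assessment recorded on the case report form. Section 9.4.4 makes severity a reporting variable: "Other AEs will be reported by severity of the adverse events (mild, moderate or severe"), alongside relatedness, frequency and MedDRA System Organ Class.

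Sections 1.3 and 4.1 schedule ALT, AST and total bilirubin on day 14 for every participant, with or without symptoms. Section 10.1.2 includes among the circumstances that may justify suspension or termination: "A study participant with hepatic enzyme elevation greater than 3 times the upper limit of normal seen on laboratory testing on day 14".

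**The concern.** A severity guide that applies only outside some other grading system is sensible if that other system exists. Laboratory toxicities usually need one, because a blood result has no direct link to daily activity or to treatment. Here the other system is missing, and a guide written for symptoms has to cover laboratory findings as well.

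Liver function is plainly a safety question in this protocol. Any baseline elevation excludes the patient (5.2, criterion 15), the sponsor reviews the first 20 participants' post-treatment liver tests before enrolment expands (8.2), and cases consistent with Hy's law go to the FDA as expedited reports (8.3.6). The day-14 tests are the only scheduled post-treatment laboratory measurement. If the severity column puts every symptom-free elevation in its lowest category, a reader of the results cannot tell a trivial rise from one large enough to be a possible ground for suspension. For the first study of this drug in this indication, that information should carry forward to a larger trial.

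**Working it through.** No arithmetic applies: the plan states no figure on this point. The check sets the sections side by side.

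**Step 1. Does the grading system exist?** The adverse-event sections (8.2 to 8.4), the analysis sections (9.4.3 and 9.4.4), the closure section (10.1.2), the abbreviations, the references and Appendix A were searched. None contains a toxicity table, a named external scale or a set of laboratory grades. Section 8.3.8 adds no event of special interest, and Appendix A holds only ultrasound criteria. Section 10.1.10 mentions a Manual of Procedures, but 8.3.3.1 speaks of a system defined in the protocol. The guide therefore covers every adverse event.

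**Step 2. Do the liver provisions supply a grade?**

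| Section | What it sets | Grade assigned? |
|---|---|---|
| 5.2, criterion 15 | Exclusion for any baseline value above ULN | No |
| 8.2 | Follow-up to resolution, referral if not normal within one month, sponsor review after 20 participants | No |
| 8.3.6 | Expedited report for Hy's law cases | No |
| 10.1.2 | Above 3 times ULN on day 14 as a possible ground for suspension | No |

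They set thresholds and actions only.

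**Step 3. Which level fits a symptom-free enzyme result above 3 times ULN?**

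- Mild: both conditions are met. No treatment is required by the result itself, and daily activity is unaffected.
- Moderate: no clear hook. There is no inconvenience and no loss of function, and the word concern is tied to therapeutic measures.
- Severe: usual activity is not interrupted and the participant is not incapacitated.

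The literal grade is mild. Nothing in the wording depends on the multiple of ULN, so a result just above ULN and one well above 3 times ULN receive the same grade.

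**Step 4. What would the reports show?**

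- The side effects and adverse events listed in 9.4.3 include no liver item, so a liver elevation recorded as an adverse event falls among the other events that 9.4.4 reports by severity.
- No part of section 9.4 plans a summary of liver-test values.
- Section 9.4.8 rules out individual listings, and 9.4.9 rules out additional exploratory analyses.
- Frequency, relatedness and System Organ Class would show that an event occurred, but not how large it was.

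Severity is thus the only planned output that reflects size, and on the literal reading it is the same for every symptom-free elevation.

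**Step 5. Is the premise secure?** The protocol does not say outright that a laboratory-only elevation is an adverse event. The definition in 8.3.1 is broad enough to include it, but 7.2 names clinical adverse events and laboratory abnormalities separately. If such elevations are not recorded as adverse events, section 9.4 plans no report of them at all, which leaves a larger gap.

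**The case against.** The strongest reply is that liver safety does not run through the severity grade. Baseline exclusion, day-14 testing, follow-up and referral, the review after 20 participants, Hy's law reporting and the ground in 10.1.2 all work from the laboratory values themselves. This stands in full. A reader might infer that a mild grade would let a liver signal go unanswered; the documents do not support that. Nor do they support saying that such a result stops the study: 10.1.2 is permissive. A mild grade beside a possible ground for suspension is not by itself a contradiction, since severity and study-level action are different questions.

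A reader might also infer that the temporary pause in 8.3.6, which is worded around the first severe event, would fail to respond. That is unproven. The pause sits in the section on serious adverse event reporting, and section 5.4 expands the abbreviation SAE as severe adverse event, so the word there may well mean serious. Seriousness under 8.3.2 includes important medical events identified by judgement, whatever their grade. The mixed use of the two words needs its own correction.

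Finally, 8.3.3.1 offers guidelines and 8.3.4 records a clinician's assessment. A clinician could argue for moderate through the word concern, or point to the further workup and treatment foreseen in 8.2. This stands against any claim that mild is certain. It does not rescue the scale: if two clinicians can grade the same result differently, the severity row still does not convey the size of an elevation.

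**Conclusion.** The concern holds as a defect in safety reporting. The grading system to which 8.3.3.1 defers is absent, the remaining guide does not suit laboratory findings, and its literal result for a symptom-free liver elevation is mild at any size. The effect falls on the 9.4.4 severity reporting, where no other planned output shows how large an elevation was.

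The scope is every symptom-free ALT, AST or bilirubin elevation in the planned sample of 40. The documents give no expected rate, so the number of participants affected cannot be stated.

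The conclusion rests on two assumptions: that laboratory-only elevations are recorded as adverse events, and that clinicians follow the guide as written. If the first fails, the elevations go unreported under section 9.4. If the second fails, grades vary with the assessor. In neither case does the plan report the size of elevations reliably.

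**What to change.** 1. In 8.3.3.1, include or cite the grading system referred to, or delete the reference.
2. State that laboratory abnormalities are recorded, and that ALT, AST and total bilirubin are graded by multiples of ULN on a published toxicity scale named in the protocol. Keep the activity-based guide for symptomatic events.
3. In 9.4.4, add a separate table of day-14 ALT, AST and total bilirubin by ULN category, with the number of participants tested as the denominator.
4. Separately, reconcile the use of severe and serious across 5.4, 8.3.3.1 and 8.3.6, so that it is clear which classification each provision relies on.

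No clinical threshold or stopping rule needs to change for the grading and reporting repair. The laboratory values are already collected and entered in the study database (10.1.9.1), so the cost is a short text edit and one table.

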8.3.3.2 RELATIONSHIP TO STUDY INTERVENTION

All adverse events (AEs) must have their relationship to study intervention assessed by the clinician who examines and evaluates the participant based on temporal relationship and his/her clinical judgment.

The degree of certainty about causality will be graded using the categories below. In a clinical trial, the study product must always be suspect.

- **Related** The AE is known to occur with the study intervention, there is a reasonable possibility that the study intervention caused the AE, or there is a temporal relationship between the study intervention and event. Reasonable possibility means that there is evidence to suggest a causal relationship between the study intervention and the AE.
- **Not Related** There is not a reasonable possibility that the administration of the study intervention caused the event, there is no temporal relationship between the study intervention and event onset, or an alternate etiology has been established.

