5.4 SCREEN FAILURES

Screen failures are defined as participants who consent to participate in the study but are not administered the study intervention (ulipristal acetate) due to either participant withdrawal from the study or change in exclusion criteria following informed consent. A minimal set of information will be kept on all screen failure participants including eligibility screening checklist, informed consent documentation, demographic questionnaire (if completed), screen failure details and any severe adverse event (SAE). This information may be used in study reports, published materials, or to respond to regulatory authorities.

Additionally, a minimal set of information will be kept for patients screened for enrollment who do not meet eligibility criteria or who do not consent to participate in the study on the study screening register.

This information includes name, date of birth, referring physician, date of referral, date of contact with patient, and patient outcome (e.g. screen out, decline to participate, enroll in study). Following completion of enrollment of study participants, this information will be de-identified with just the number of patients in each outcome (screen out, decline to participate, enroll in study) for use in study reports, published materials, or to respond to regulatory authorities.

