6 STUDY INTERVENTION

6.1 STUDY INTERVENTION(S) ADMINISTRATION

6.1.1 STUDY INTERVENTION DESCRIPTION

The study intervention will involve administration of 90mg UPA (three 30mg oral tablets) followed by 800mcg misoprostol (four 200mcg tablets) vaginally 6 to 18 hours after.

- Information regarding UPA 30mg oral tablet is detailed in the full prescribing information from the FDA. Use of UPA for this purpose is being studied under an IND (pending).
- Information regarding misoprostol 200mcg tablet is detailed in the full prescribing information
 from the FDA. While the FDA approves misoprostol for treatment of gastric ulcers, the dose and
 route of 800mcg misoprostol vaginally for medication abortion or medication treatment of early
 pregnancy loss has been studied extensively and is the most successful regimen to date [30, 31].

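### The Related and Not Related definitions in 8.3.3.2 overlap, and the target of attribution changes between sections, so the same adverse event can be coded either way

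*Combined protocol and SAP*

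**What the plan says.** **Definitions (8.3.3.2).** The examining clinician assesses every AE, using timing and clinical judgment.

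- *Related* opens with two alternatives, "The AE is known to occur with the study intervention, there is a reasonable possibility that the study intervention caused the AE", and adds a third: "or there is a temporal relationship between the study intervention and event".
- *Not Related* opens with "There is not a reasonable possibility that the administration of the study intervention caused the event" and continues: "there is no temporal relationship between the study intervention and event onset, or an alternate etiology has been established".
- Ahead of both stands a general presumption: "In a clinical trial, the study product must always be suspect".

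**Target of attribution.**

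- 4.1 and 5.4 use study intervention to mean UPA.
- 6.1.1 includes misoprostol: "The study intervention will involve administration of 90mg UPA (three 30mg oral tablets) followed by 800mcg misoprostol". The adherence definition in 9.4.2 does the same.
- 8.3.4 has the CRF record relationship to the study product.
- 9.4.4 reports events as "related or not related to the study protocol".

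**Use.** 9.4.4 plans the severity and relatedness breakdown for other AEs, after setting apart the side effects and events listed in 9.4.3, which are planned as N and % only. 8.3.6 requires each SAE report to assess whether there is a reasonable possibility that the study intervention caused the event. 8.3.3.3 judges expectedness against the risk information for the study intervention.

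**The concern.** A two-level causality scale works only if each event belongs to one level and everyone is judging the same cause. Neither condition holds here. The two lists are not complements, because each is joined by *or* and they use different criteria. The target is also worded differently in the definition, on the CRF and in the analysis.

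This matters more than it would in a controlled trial. All participants are to receive UPA and be instructed to take misoprostol some hours later, with no comparison group (4.1, 4.2). Symptoms from UPA, from misoprostol and from expulsion therefore cannot be separated by comparing arms, and attribution is the main tool left for doing so. The protocol also describes this as the first study of UPA for this indication. A relatedness column that depends on which clause the assessor happened to apply would say little about UPA to those planning the larger trial.

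**Working it through.** No sample size, power or rate in the plan bears on this point, so there is no stated figure to reproduce. The check is one of logic.

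**Step 1: overlap.** Take the four criteria in 8.3.3.2 as present or absent:

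- K = known to occur with the intervention
- R = reasonable possibility of causation
- T = temporal relationship
- A = alternate etiology established

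Read as written:

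- Related = K or R or T
- Not Related = (not R) or (not T) or A

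There are 2 × 2 × 2 × 2 = 16 combinations.

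| Set of combinations | Total | Meet both | Only Related | Only Not Related | Neither |
|---|---|---|---|---|---|
| All | 16 | 12 | 2 | 2 | 0 |
| Excluding R together with A | 12 | 8 | 2 | 2 | 0 |
| Timing fits (T = 1) | 8 | 6 | 2 | 0 | 0 |
| Timing fits, excluding R together with A | 6 | 4 | 2 | 0 | 0 |

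Only Related requires R and T present and A absent. Only Not Related requires K, R and T all absent. Once timing fits, no event is Not Related without also being Related. The second and fourth rows show that the overlap survives if an established other cause is taken to rule out a reasonable possibility.

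**Step 2: two examples.**

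- An accidental injury two days after UPA: T is present and R is absent. It is Related by timing and Not Related for want of a reasonable possibility. The alternate-etiology clause is not needed to produce the conflict.
- A day-14 liver-test abnormality recorded as an AE, for which another cause is then established: Related by timing, Not Related by alternate etiology. It is not among the items in 9.4.3, so it falls in the 9.4.4 split.

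**Step 3: target.** Suppose the overlap were cured and the true cause agreed. The code would still depend on the target:

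| Agreed cause | Target: UPA | Target: UPA + misoprostol | Target: study protocol, read to include procedures |
|---|---|---|---|
| Misoprostol | Not Related | Related | Related |
| Study blood draw (bruising, a risk named in 2.3.1) | Not Related | Not Related | Related |

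*Study product* on the CRF could mean either of the first two targets. What the form collects is therefore not clearly what 9.4.4 says it will report.

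**The case against.** **Judgment and the presumption of suspicion.** The clinician decides, and the study product is always to be suspected, so doubtful events lean towards Related. That direction is real, but it is not written as a precedence rule. Applied as one, it would make nearly every post-dose event Related and leave Not Related almost empty.

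**SAE reporting is largely protected.** Every SAE goes to the sponsor whether or not it is thought related, with a reasonable-possibility assessment (8.3.6). This stands: only the target is unclear there. The pause after a first severe adverse event (8.3.6) and the day-14 liver-enzyme circumstance (10.1.2) do not refer to relatedness.

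**Little rests on the table.** AEs are a secondary, hypothesis-generating outcome with no formal testing (9.1, 9.4.1). True, and this limits the seriousness without making the codes interpretable.

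**Stronger readings the documents do not support.**

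- A reader might infer that almost every event meets both definitions because misoprostol or expulsion is always another possible cause. The clause requires an other cause to be *established*, not merely possible. Where the intervention includes misoprostol, misoprostol is not an other cause at all.
- A reader might apply the UPA rates in 8.3.5 (headache 18%, nausea 12%, abdominal pain 12%) to 40 women, giving 0.18 × 40 = 7.2 and 0.12 × 40 = 4.8, and conclude that some 5 to 7 women per symptom would be ambiguous in the relatedness table. Headache and nausea are listed in 9.4.3 and are not planned to be split by relatedness. Abdominal pain is close to the listed severe cramping. The main analysis of side effects and AEs in 9.3 is also restricted to adherent participants who complete all visits, not all 40.
- A reader might say the related share could lie anywhere from 0% to 100%. That is a logical bound, and nothing in the documents makes either end likely.

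**Conclusion.** The point holds as a contradiction in a stated rule. The two definitions overlap with no written precedence, and the target takes four forms across 4.1/5.4, 6.1.1/9.4.2, 8.3.4 and 9.4.4. Either code for an event that meets both definitions is consistent with the protocol.

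The reach is limited to the relatedness recorded for all AEs, the 9.4.4 split of other AEs, and, through the target alone, the SAE assessment in 8.3.6 and expectedness in 8.3.3.3. The listed 9.4.3 frequencies, the primary feasibility outcomes and the sample size are unaffected.

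The size is expressed in logical cases: 12 of 16 combinations meet both definitions, or 6 of 8 when timing fits. This rests on reading each *or* literally and treating each criterion as simply present or absent. It gives no estimate of how many events would be miscoded, and the documents give no figure from which to make one. It should be corrected because the fix is cheap and there is no control arm to fall back on.

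**What to change.** 1. In 8.3.3.2, define Related as a reasonable possibility that the named target caused the event, and Not Related as no such reasonable possibility. This is the criterion 8.3.6 already uses. Keep timing, known effects and alternate etiology as evidence to weigh, not as sufficient conditions.
2. Name the target once and use the same words in 8.3.3.2, 8.3.4, 8.3.6, 9.4.4 and the CRF. Preferably record two attributions per AE, one to UPA and one to misoprostol or expulsion, and state which one 8.3.6 uses and which 9.4.4 tabulates. If procedures such as blood draws are meant to be covered, say so.
3. Optionally, tabulate AEs that began before misoprostol, limited to events with a recorded onset time. The AE CRF collects onset (8.3.4) and Visit 2 collects misoprostol time (4.1), but the plan does not say that onset is recorded for each side effect listed in 9.4.3.

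The cost is a wording amendment and one extra CRF item. Splitting attribution between UPA and misoprostol or expulsion will remain partly a matter of judgment.
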